## **8. SAFETY**

No inferential statistics will be performed on the safety endpoints.

All Case Report Form (CRF) data will be listed by subject and chronologically by assessment time points. This will include rechecks, unscheduled assessments, and early termination results.

Applicable continuous variables will be summarized using the number of observations (n), mean, SD, minimum, median, and maximum. Frequency counts will be reported for categorical data, when appropriate. The placebo subjects from all cohorts will be pooled into a single group for summarization.

The level of precision will be presented as follows: minimum/maximum in the same precision as in the database, mean/median in one more precision level than minimum/maximum, SD in one more precision level than mean/median, and n will be presented as an integer.

For laboratory, ECGs, and vital signs, where individual data points are missing because of dropouts or other reasons, the data will be summarized based on reduced denominators.

### **8.1 Subject Discontinuation**

Subject disposition will be listed and summarized by number of subjects dosed, completed, and discontinued the study with discontinuation reasons by dose level, pooled placebo, and for overall the study.

### **8.2 Demographics**

Demographic data will be listed and summarized. Descriptive statistics will be calculated for continuous variables (age, weight, height, and body mass index [BMI]) by dose level, pooled placebo, and for overall the study. Frequency counts will be provided for categorical variables (race, ethnicity, and sex) by dose level, pooled placebo, and for overall the study. Age will be derived from date of birth to date of first dosing.

### **8.3 Adverse Events**

All AEs occurring during this clinical trial will be coded using the MedDRA®, Version 21.0 or a later version if available. All AEs captured in the database will be listed in by-subject data listings including verbatim term, coded term, dose level, placebo, severity, relationship to study drug, and action; however, only treatment-

emergent AEs (TEAEs) will be summarized. Any non-drug procedure performed due to an AE will be listed by subject.

A TEAE is defined as an AE that is starting or worsening at the time of or after the study drug dose administration. If an AE increases in severity, that AE will be given a resolution date and time and a new record will be initiated with the new severity. If the severity of an AE remains the same or decreases, the AE will be kept open through to resolution and the maximum severity will be recorded. If the onset time of an AE is missing and the onset date is the same as the treatment dosing date or does not fall on a dosing date, the AE will be considered treatment-emergent. If the onset date of an AE is missing, then the AE will be considered treatment-emergent.

TEAEs will be tabulated by system organ class (SOC) and preferred term. Summary tables will include number of subjects reporting the TEAE and corresponding percentage by dose level, pooled placebo, and overall the study. The number of TEAEs will be summarized in a similar way. Percentages will be based on the total number of subjects dosed or total number of TEAEs, respectively, for each dose level, pooled placebo, or overall the study, as appropriate. In addition, the number of TEAEs will be summarized by severity and relationship to study drug.

If present, serious adverse events (SAEs) will be listed, displayed in a table, and a narrative included in the study CSR.

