### **9.2 Study Endpoints**

The primary endpoints of the study will be the number and severity of TEAEs following single IV bolus doses of E-WE thrombin and placebo.

The secondary endpoints are the PD (i.e., APC-PCI) of E-WE thrombin following single IV bolus doses. PD will act as a surrogate for PK of E-WE thrombin.

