### 2.2 Endpoints

The **primary endpoints** of the study will be the number and severity of treatment-emergent adverse events (TEAEs) following single IV bolus doses of E-WE thrombin and placebo. In addition, physical examinations, vital signs, electrocardiograms (ECGs), clinical laboratory tests (including coagulation), thrombin time, immunogenicity, and injection site reaction will be assessed throughout the study.

The **secondary endpoints** are the PD (i.e., APC-PCI) of E-WE thrombin following single IV bolus doses. PD will act as a surrogate for pharmacokinetics (PK) of E-WE thrombin.

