Note: 0.5 mcg/kg: 0.5 mcg/kg E-WE thrombin (IV bolus)

1.0 mcg/kg: 1.0 mcg/kg E-WE thrombin (IV bolus)

2.0 mcg/kg: 2.0 mcg/kg E-WE thrombin (IV bolus)

4.0 mcg/kg: 4.0 mcg/kg E-WE thrombin (IV bolus)

Pooled Placebo: Placebo Solution (IV bolus)

\*Adverse events are classified according to MedDRA Version 21.0. ^ = Treatment-emergent adverse events

If a subject experience the same adverse event (AE) at more than one level of severity during a treatment, each AE is counted separately. If a subject experience the same AE at more than one level of drug relationship during a treatment, each AE is counted separately.

Severity/Intensity: Grade 1 = Mild; Grade 2 = Moderate; Grade 3 = Severe; Grade 4 = Potentially life-threatening

Program: /CAXXXXX/sas\_prg/stsas/tab\_PROGRAMNAME.sas DDMMYYYY HH:MM

Table 14.3.2.1 Serious Adverse Events (Safety Population)

Dose Level/ Placebo	Subject Number	Adverse Event	Onset		Frequency	Severity/ Intensity	Serious	Outcome	Relationship to Study Drug	Action
			Date	Time						
XXX <units>	X	XXXXXXXXXX	DDMMYYYY	XX:XX	XXXXXXXXXX	XXXX	XXXX	Resolved	XXXXXXXXXX	XXXXXXXXXX

Programmer Note: If no SAE, then table will contain the statement: "There were no serious adverse events recorded during the study."

Note: 0.5 mcg/kg: 0.5 mcg/kg E-WE thrombin (IV bolus)  
 1.0 mcg/kg: 1.0 mcg/kg E-WE thrombin (IV bolus)  
 2.0 mcg/kg: 2.0 mcg/kg E-WE thrombin (IV bolus)  
 4.0 mcg/kg: 4.0 mcg/kg E-WE thrombin (IV bolus)  
 Placebo: Placebo Solution (IV bolus)

Program: /AAXXXXX/sas\_prg/stsas/tab\_PROGRAMNAME.sas DDMMYYYY HH:MM

Tables 14.3.4.1 to 14.3.4.4 will have the following format:

Table 14.3.4.1 Out-of-Range Values and Recheck Results - Serum Chemistry (Safety Population)

Dose Level/ Placebo	Subject Number	Age#/ Sex	Study Period	Day	Hour	Date	Time	Parameter1 <Range> (Unit)	Parameter2 <Range> (Unit)	Parameter3 <Range> (Unit)	Parameter4 <Range> (Unit)	Parameter5 <Range> (Unit)
XXX <units>	X	XX/X	Screen	.	.	DDMMYYYY	HH:MM:SS	XX HN				XX IN
			1	-X	-XX.XX	DDMMYYYY	HH:MM:SS	XX LY-	XX IN	XX HN	XX LYR+	
			Recheck			DDMMYYYY	HH:MM:SS				XX	

Programmer Notes: Replace Parameter1, 2 etc. with actual lab tests in the study. Sort unscheduled assessment and early termination chronologically with other scheduled assessments and rechecks. Recheck should be sorted with the scheduled time point the recheck is for.

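### A post-dose adverse event that worsens is counted again at each grade it reaches, while one that holds steady or improves is counted once, so the TEAE event counts depend on the path of the event

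*SAP*

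**What the plan says.** Protocol Section 9.2 sets the endpoint: "The primary endpoints of the study will be the number and severity of TEAEs following single IV bolus doses of E-WE thrombin and placebo". SAP Section 2.2 repeats it.

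SAP Section 8.3 has two record rules. If severity rises, "that AE will be given a resolution date and time and a new record will be initiated with the new severity". If severity is unchanged or falls, "the AE will be kept open through to resolution and the maximum severity will be recorded". The same section gives the definition: "A TEAE is defined as an AE that is starting or worsening at the time of or after the study drug dose administration". It then plans a tabulation in which "the number of TEAEs will be summarized by severity and relationship to study drug", and bases event percentages on the total number of TEAEs.

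The shell of Table 14.3.1.3 (SAP Section 11.2) carries the footnote: "If a subject experience the same adverse event (AE) at more than one level of severity during a treatment, each AE is counted separately". A companion sentence does the same for different levels of drug relationship. The footnotes of Tables 12-1 and 14.3.1.1 instead count a subject once per category.

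The protocol's AE sections (11.1.8 and 12.1.3) contain no record-splitting rule. Neither document links the split records, collapses them into one episode, or plans a table of subjects by worst grade.

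**The concern.** Two episodes with the same peak can give different counts. A headache that climbs through Grades 1, 2 and 3 after dosing is three TEAEs, one in each grade column. A headache that starts at Grade 3 and fades is one TEAE at Grade 3. The difference comes from how the record is kept, not from how many events occurred.

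This bears on the primary endpoint as worded. Tables 14.3.1.2 and 14.3.1.3 are where the number of TEAEs is reported, and 14.3.1.3 is the only planned AE summary by severity. With four active subjects per dose level, one split episode changes a cell visibly.

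There are two side effects. The AE listing (Appendix 16.2.7.1.1) will show a resolution date and a shortened duration for an event that was still going on, although Protocol Section 11.1.8.3 asks for the duration and outcome of each event. And because the grade columns of Table 14.3.1.3 count events, the severity half of the endpoint has no subject-level display.

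**Working it through.** **Plan's own figure.** The only related figure is the planned sample size: 6 + 3 × 5 = 21 subjects, of whom 4 × 4 = 16 are active and 2 + 3 × 1 = 5 are placebo. This agrees with Protocol Section 10.3.1. The plan states no expected TEAE count, and SAP Section 8 excludes inferential statistics on safety, so there is no power or error rate to recompute.

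**Records per episode.** I applied the SAP 8.3 rule to grade paths with post-dose onset, opening a new record each time a grade above the previous highest is reached. The first record qualifies as a TEAE because it starts after dosing, and each later one because it worsens.

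| Grade path | Records under the SAP rule | Events if counted per episode |
|---|---|---|
| steady at 1 | 1 | 1 |
| 3, then 1 | 1 | 1 |
| 1, 2 | 2 | 1 |
| 1, 3 | 2 | 1 |
| 1, 2, 3 | 3 | 1 |
| 1, 2, 3, 4 | 4 | 1 |

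**One dose level (assumed data).** There are four subjects with one post-dose episode each. Three episodes stay at Grade 1 and the fourth follows the path shown. Cells are total events, then counts at Grades 1/2/3/4.

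| Fourth episode | SAP rule | One event per episode, at maximum grade |
|---|---|---|
| 1, 2 | 5 (4/1/0/0) | 4 (3/1/0/0) |
| 1, 2, 3 | 6 (4/1/1/0) | 4 (3/0/1/0) |
| 1, 2, 3, 4 | 7 (4/1/1/1) | 4 (3/0/0/1) |
| 3, then 1 | 4 (3/0/1/0) | 4 (3/0/1/0) |

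Every extra record lies below the peak grade of its episode. The number of subjects with a TEAE is 4 of 4 in every row under both rules.

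**Percentages in Table 14.3.1.2.** These use total TEAEs as denominator. If the 1, 2, 3 episode is the only one under its preferred term, that term takes 3/6 = 50.0% of events instead of 1/4 = 25.0%.

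**Severity mix.** The share of events at Grade 3 or above is not itself a planned statistic, but a reader could derive it from Table 14.3.1.3. For the 1, 2, 3 path it is 1/6 = 16.7% instead of 1/4 = 25.0%. For the 1, 2, 3, 4 path it is 2/7 = 28.6% instead of 1/4 = 25.0%. The direction is not fixed.

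**Range.** If a share w of post-dose episodes worsens and each of those has k upward steps, the event count is multiplied by 1 + w × k. The documents give neither w nor k, so both are assumptions:

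- w = 10%: 1.10 (k = 1) to 1.30 (k = 3)
- w = 25%: 1.25 to 1.75
- w = 50%: 1.50 to 2.50

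**Pre-dose onset.** An AE that begins before dosing and worsens once afterwards gives one TEAE record, so it is not double counted. If it worsens twice after dosing it gives two. No stated rule limits this to one.

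**The case against.** The convention is disclosed and fits the SAP's own definition, which treats worsening as treatment-emergent. Counting by episode is therefore an alternative, not the correction of a contradiction.

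The display offers safeguards. Table 14.3.1.3 puts the number of subjects with TEAEs beside the number of TEAEs, by preferred term and dose level, so a row with one subject and three events at three grades reveals the repetition. The AE table planned for the report text, Table 12-1, counts subjects. Listings give onset and resolution times, and with 21 subjects split episodes could be pieced together by eye. No test or interval is affected.

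All of this stands, and it limits the importance of the point. It does not make the event counts independent of path, and it does not supply severity by subject.

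A reader might go further and infer four things that the documents do not support:

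- **That the worst events are diluted in general.** The severity table shows counts without percentages, and the derived share can move either way.
- **That dose levels are compared unfairly because worsening concentrates at active doses.** This is plausible, but the documents give no frequency of worsening by dose.
- **That dose-escalation criterion 4b or stopping criterion 5.II.b in Protocol Section 10.4.1.4 is compromised.** Those criteria count subjects and rest on review of accumulating data. Splitting a record cannot change whether a subject reached a grade.
- **That the incidence tables are inflated.** Tables 12-1 and 14.3.1.1 count each subject once per category.

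**Conclusion.** The point holds in a limited form. Under SAP Section 8.3 and the Table 14.3.1.3 footnote, a post-dose AE that worsens is counted at each grade it reaches, up to four times, while one that stays level or improves is counted once. The event counts in Tables 14.3.1.2 and 14.3.1.3, and the percentages in 14.3.1.2, are therefore path-dependent.

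In a dose level with four episodes, one worsening episode adds between one and three events. The overall effect is unknown because the documents do not say how often events will worsen; if none worsens after a post-dose onset, there is no effect. The ceiling of four assumes that a new record opens only when a new highest grade is reached. The SAP does not say what happens when an event eases and then worsens again.

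This is a cheap improvement to a counting rule in a descriptive study. It does not threaten the subject-level safety results or the conduct of dose escalation.

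**What to change.** Change SAP Section 8.3 and two table shells, preferably before unblinding so that the rule is prespecified:

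- Keep the stepwise records in the listings, link them by an episode identifier, and show the true end date and duration of the episode.
- In Tables 14.3.1.2 and 14.3.1.3, count each continuous episode once, at its maximum post-dose severity and its strongest post-dose relationship to study drug. Naming the relationship matters because the present footnote also splits on it.
- State that a pre-dose AE that worsens after dosing counts as one TEAE, however many times it worsens.
- Amend the Table 14.3.1.3 footnote to match.
- Add one block giving the number of subjects by worst grade, by dose level and pooled placebo.

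The cost is some SAP wording, one linking variable and one small table block, with no new data. The downside is that the counts become less comparable with studies reported under record splitting. Keeping the record-level counts as a supportive display meets that.

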#### 10.1.1 Confinement, Return Visits, and Follow-Up

Subjects will be housed on Day -1, at the time indicated by the CRU, until after the 24-hour blood draw and/or study procedures as indicated in the Study Events Flow Chart ([Section 6](#)). At all times, a subject may be required to remain at the CRU for longer at the discretion of the PI or designee.

Subjects (including those who terminate early) will return on Days 14 and 28 for follow-up procedures (coagulation sample collection, thrombin time measurement, and immunogenicity sample collection) and to determine if any AE has occurred since the last study visit). Subjects who terminate the study early will be asked to continue aPTT and thrombin time monitoring as scheduled until Day 28.

Any subjects for whom aPTT and/or thrombin time did not reach  $\pm 10\%$  of the baseline value or within the normal range by Day 14, will return every 7 days ( $\pm 2$  days) until aPTT and thrombin time reach  $\pm 10\%$  of the baseline value or within the normal range and for a FU visit (i.e., follow-up procedures and AE evaluation listed on Day 28 will be repeated) 7 days ( $\pm 2$  days) after it was reached.

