### **10.2.3 Treatment Period (Day 1 to Day 2)**

#### **10.2.3.1 Single-dose Administration (Day 1) and Study Procedures (Days 1 to 2)**

On the morning of Day 1, predose evaluations will be obtained.

Subjects will receive a single IV bolus of E-WE thrombin or placebo on the morning of Day 1. See [Section 10.4.1](#) and [Section 10.4.3](#) for planned dose levels and details.

Safety and tolerability will be monitored throughout the treatment period as listed in the Study Events Flow Chart ([Section 6](#)).

Blood samples for PD assessment (see [Section 11.3](#)) will be collected at the time points as listed in the Study Events Flow Chart ([Section 6](#)).

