##### **11.1.8.2 Monitoring**

Subjects will be monitored throughout confinement for adverse reactions to the study drug and/or procedures. Subjects will be asked how they are feeling and encouraged to report AEs during confinement and at each follow-up visit.

AEs (whether serious or non-serious) and clinically significant abnormal laboratory test value(s) will be evaluated by the PI or designee and treated and/or followed up until the symptoms or value(s) return to normal, or acceptable levels, as judged by the PI or designee.

Treatment of SAEs will be performed by a physician, either at Celerion or at a nearby hospital emergency room. Where appropriate, medical test(s) and/or examination(s) will be performed to document resolution of event(s). Outcome may be classified as resolved, improved, unchanged, worse, fatal, or unknown (lost to follow-up).

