### 11.1.8.3 Reporting

All AEs that occurred during this clinical trial will be recorded. AEs will be coded using the most current version of MedDRA® available at Celerion.

The PI or designee will review each event and assess its relationship to drug treatment (unrelated, unlikely, possibly, probably, or likely,). Each sign or symptom reported will be graded on the FDA (Center for Biologics Evaluation and Research) toxicity grading scale for healthy volunteers 4-point severity scale (Grade 1, 2, 3 and 4) [8]. The date and time of onset, time relationship to drug dosing, duration, and outcome of each event will be noted.

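### The SAP's rule for a missing onset time makes an adverse event with a known pre-dose date treatment-emergent, against the SAP's own definition

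*SAP*

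**What the plan says.** SAP 8.3 opens with the definition: "A TEAE is defined as an AE that is starting or worsening at the time of or after the study drug dose administration". It then gives two fallback rules for incomplete onset information. For an event without an onset time, the rule looks at the day on which it began: if that day "is the same as the treatment dosing date or does not fall on a dosing date, the AE will be considered treatment-emergent". When the date itself is missing: "If the onset date of an AE is missing, then the AE will be considered treatment-emergent".

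SAP 8.3 also states that all adverse events are listed but only treatment-emergent ones are summarised. An event that increases in severity is closed, and a new record is opened at the new severity.

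SAP 2.2 says the primary endpoints "will be the number and severity of treatment-emergent adverse events (TEAEs) following single IV bolus doses". Protocol 9.2 names the same endpoint. The protocol's adverse event sections (11.1.8 and 12.1.3) give no definition of treatment-emergent, so SAP 8.3 is the operative text.

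On dosing, Protocol 10.2.3.1 says: "Subjects will receive a single IV bolus of E-WE thrombin or placebo on the morning of Day 1". Each subject therefore has a single dosing date.

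**The concern.** The second condition of the missing-time rule asks only that the onset date differ from the dosing date. It does not ask that the onset date be later. A headache dated Day -1 with no clock time meets that condition and is flagged treatment-emergent, although its date already shows that it began before dosing.

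Pre-dose adverse events can arise in this trial. Protocol 10.1.1 says: "Subjects will be housed on Day -1, at the time indicated by the CRU, until after the 24-hour blood draw". Protocol 11.1.8.2 adds: "Subjects will be monitored throughout confinement for adverse reactions to the study drug and/or procedures". Protocol 11.1.8.3 has all events during the trial recorded, and screening may start up to 28 days before dosing. SAP 8.8 plans symptom-driven examinations at check-in and allows abnormal findings to be reported as adverse events. The adverse event listing shells carry a treatment-emergent column, so the SAP itself expects some recorded events not to be treatment-emergent.

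At stake is the primary-endpoint display. A pre-dose event caught by the rule would be counted in Tables 12-1 and 14.3.1.1 to 14.3.1.3 under a dose level or under pooled placebo.

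**Working it through.** **Logic check.** Take an event whose onset time is missing and whose pre-dose record has not worsened, with Day 1 as the only dosing date. The missing-time rule returns treatment-emergent if day = 1 or day ≠ 1. One of these is true for any known day.

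| Onset date | Missing-time or missing-date rule | SAP definition | Agreement |
|---|---|---|---|
| Day -28 | emergent | not emergent | conflict |
| Day -14 | emergent | not emergent | conflict |
| Day -1 | emergent | not emergent | conflict |
| Day 1 | emergent | cannot be decided without a time | conservative default |
| Day 2 | emergent | emergent | agree |
| Day 14 | emergent | emergent | agree |
| Day 28 | emergent | emergent | agree |
| Missing | emergent | cannot be decided | conservative default |

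The conflict arises on every known pre-dose date tested and on no post-dose date. The defaults for Day 1 and for a missing date are reasonable, because there the timing really is unknown.

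**Worsening does not remove the conflict.** Under the new-record convention, an event that begins on Day -1 and worsens after dosing gives two records. The new one is treatment-emergent by definition. The pre-dose one is not, yet the missing-time rule flags it as well.

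**Size of one misclassified event.** The planned numbers come from Protocol 10.3.1:

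- Active subjects per dose level: 4.
- Pooled placebo: 2 + 1 + 1 + 1 = 5.
- Overall: 6 + 3 × 5 = 21, which matches the protocol's stated total.

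Subject incidence, for a subject with no other treatment-emergent event in that table row:

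- Dose level: 1/4 = 25.0 percentage points.
- Pooled placebo: 1/5 = 20.0 percentage points.
- Overall column: 1/21 = 4.8 percentage points.

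Event count (Table 14.3.1.2): always +1, whether or not the subject has other events. With k true events in the group, the relative increase is 1/k. The documents give no k. Assuming a range of 2 to 6:

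- k = 2: 1/2 = +50%.
- k = 4: 1/4 = +25%.
- k = 6: 1/6 = +17%.

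**The case against.** The strongest reply is that this is loose wording and not a decision to count pre-dose events. The definition comes first in the paragraph, and the missing-time sentence is a fallback for cases the definition cannot settle. A known pre-dose date settles the matter without a clock time, so a sensible reader would take the second condition to mean later dates. That may well be the intention. But nothing in either document says so, and a programmer who codes the sentence as written would flag pre-dose events.

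The second reply is that the case will hardly ever occur. Protocol 11.1.8.3 requires that "The date and time of onset, time relationship to drug dosing, duration, and outcome of each event will be noted". Protocol 13.3 prescribes a full quality control check and edit checks for missing data before lock, and 13.6 adds validation against contradictory data. Pre-dose findings may also be entered as medical history under SAP 8.8. All this is accurate and makes the case uncommon, possibly absent. It does not make the rule give the right answer when the case does occur: a missing-time rule exists for times that stay missing, and this one makes no use of the recorded relationship to dosing.

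The third reply is that the effect is mild. No inferential test is planned, and the escalation and stopping criteria in Protocol 10.4.1.4 do not use the treatment-emergent flag. The listings show the onset date, so the case could be noticed, and the rule can only add events. The first three points stand. The last is only partly reassuring: an extra event in pooled placebo raises the comparator and can make the active dose levels look better.

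Finally, any single event moves a group of four by 25 points, so that figure reflects group size and not anything peculiar to this rule. That is fair. It measures what one error would do and is not an expected impact.

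**Conclusion.** The point holds. As written, the missing-time rule contradicts the definition in its own paragraph for every known pre-dose onset date, and no other text limits it. It should be corrected, because it decides which events enter the primary-endpoint tables.

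The effect is conditional. It needs an adverse event recorded with a pre-dose date, a missing onset time, and survival of both gaps through data cleaning. The documents give no frequency for this, and it may be zero. The incidence shifts calculated above assume the planned group sizes and a subject with no other event in the row; the relative increases in event count assume 2 to 6 true events per group. Conclusions about dose escalation are not affected through this flag.

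**What to change.** Replace the missing-time sentence in SAP 8.3 with wording to this effect: *When the onset time is missing, an event is treatment-emergent if its onset date is on or after the dosing date. If its onset date precedes the dosing date, that record is not treatment-emergent; should the event worsen at or after dosing, only the new record opened at the worsening is flagged.* Keep the existing rule for a missing onset date.

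The cost is one sentence in the SAP and one date condition in the derivation of the treatment-emergent flag. No protocol amendment is needed. The change should be made before database lock and unblinding, so that no primary-endpoint event has to be reclassified once treatment is known; SAP section 1 would require such a late change to be documented in the clinical study report.
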